## CONFIDENTIAL

207660

Overview of Study Design and Key Features	
	
muscles that act on the finger (including thumb flexors) and wrist flexors, and 160 units into the muscles that act on the elbow flexors. A total of 400 units of the product will be injected.
 
 
• In the 240-unit group, 240 units of the product will be injected into the muscles that act on the finger (including thumb flexors) and wrist flexors. Placebo will be injected into the muscles that act on the elbow flexors. A total of 240 units of the product will be injected.
 
• In the Open-label phase, a total of 400 units will be injected in both groups. 
 
• The product can be injected up to 3 times after completion of Part 1 in the blind phase. Participants whom the investigator considers as eligible for the injections will be treated. The next injections cannot be performed until the eligibility of the participant has been confirmed by the investigator.
 
• The muscle to be injected and the dose will be decided by the investigator based on the patient's symptoms, and a total dose of 400 units of the product will be injected in a divided dose. For the muscles that the investigator considers as unnecessary to be treated, an injection may be skipped. The involving muscle and the dose do not have to be same each time always.
 
 
 

Treatment Assignment	
 
• Number of participants (randomized participants): 120 (60 per group)
 
• GSK RandAll NG will be used to generate the randomization schedule.
 
• The randomization will be stratified by the MAS score (3 or 4) in the elbow flexors at Day1
 

Interim Analysis	
 
• Interim analysis is planned in this study as described in 3.1.
 

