**4. ANALYSIS POPULATIONS**

Population	Definition / Criteria	Analyses Evaluated
Screened	
 
Comprise of all screened participants
 
	
 
Study Population
 

Enrolled	
 
Comprise of all participants who meet the eligibility criteria at a screening and Day 1 visit.
 
	
 
Study Population
 

Intent-To-Treat 1 (ITT1)	
 
This population consists of all participants who are randomized in the study and who have at least 1 post-baseline efficacy assessment:
 
ITT is the primary efficacy analysis population, and the participants will be analyzed in line with the randomized treatment group
 
Any participant who receives a study treatment randomization number will be considered to have been randomized.
 
	
 
Study Population
 
Efficacy
 

ITT2	
 
This population consists of all participants in ITT1 population, who have at least 2 study treatments and who have at least 1 efficacy assessment after the 2nd treatment.
 
	
 
Study Population
 
Efficacy
 

ITT3	
 
This population consists of all participants in ITT2 population, who have at least 3 study treatments and who have at least 1 efficacy assessment after the 3rd treatment.
 
	
 
Study Population
 
Efficacy
 

ITT4	
 
This population consists of all participants in ITT3 population, who have 4 study treatments and who have at least 1 efficacy assessment after the 4th treatment.
 
	
 
Study Population
 
Efficacy
 

Safety1	
 
This population consists of all participants who are randomized in the study and who receive study treatment at least once
 
The participants will be analyzed based on the treatment actually given.
 
	
 
Safety
 

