### 8.1. Adverse Events Analyses

Adverse events analyses including the analysis of adverse events (AEs), Serious (SAEs) and other significant AEs will be based on GSK Core Data Standards. The details of the planned displays are provided in [Appendix 12: List of Data Displays](#).

Adverse events that occurred in the overall study period, blinded period and open-label period will be summarized for each treatment group. The treatment group is based on dose actually given in blind period. For the blinded period, 2 patterns of analyses on adverse events will be performed, one is on adverse events that occurred between the initial dose and the first dose in the open-label period (or at the completion of study if no dose is given in the open-label period or at the study withdrawal), and another one is on adverse events that occurred within 84 days from the initial dose.

Overall study period (Treatment Emergent AEs)

Blind phase

1. AEs occurred between the initial dose and the first dose in the open-label period (or at the completion of study if no dose is given in the open-label period or at the study withdrawal)
2. AEs occurred within 84 days from the initial dose

Open-label phase

- 3.01. AEs occurred during 2nd treatment cycle.
- 3.02. AEs occurred during 3rd treatment cycle.
- 3.03. AEs occurred during 4th treatment cycle.

The number and percentages of participants who experience at least one AE will be presented for each category of AE listed as below by treatment group.

- All Treatment Emergent AEs (by SOC and PT, by SOC, PT and Maximum Intensity)
- Common AEs ( $\geq 3\%$ ) (by overall frequency)
- Drug Related AEs (by SOC and PT, by SOC, PT and Maximum Intensity)
- Non-Fatal Serious AEs
- Drug Related Non-Fatal Serious AEs
- AEs Leading to Withdrawal from Study (by SOC and PT)
- Most Common Serious Drug Related AEs (by overall frequency)
- Most Common Non-Serious Drug Related AEs (by overall frequency)
- Common ( $\geq 5\%$ ) Non-Serious AEs (by SOC and PT)
  - Number of Participant and Occurrences will be presented.

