### 10.4.2. Study Phases for Adverse Events

Flag	Definition
Treatment Emergent	
 
First Study Treatment Date ≤ AE Start Date ≤ Final Visit Date/Early Withdrawal Date
 

Blind phase (until second dose)	
 
First Study Treatment Date ≤ AE Start Date ≤ Second Study Treatment Date AND AE Start Time < Second Study Treatment Time IF AE Start Time is collected
 
First Study Treatment Date ≤ AE Start Date < Second Study Treatment Date IF AE Start Time is not collect.
 

Blind phase (within 84 days)	
 
First Study Treatment Date ≤ AE Start Date ≤ First Study Treatment Date + 83 days
 

Open-Label Phase (2nd Treatment)	
 
Second Study Treatment Date ≤ AE Start Date ≤ Third Study Treatment Date AND Second Study Treatment Time ≤ AE Start Time < Third Study Treatment Time IF AE Start Time is collected
 
Second Study Treatment Date ≤ AE Start Date < Third Study Treatment Date IF AE Start Time is not collected
 

Open-Label Phase (3rd Treatment)	
 
Third Study Treatment Date ≤ AE Start Date ≤ Fourth Study Treatment Date AND Third Study Time ≤ AE Start Time < Fourth Study Treatment Time IF AE Start Time is collected
 
Third Study Treatment Date ≤ AE Start Date < Fourth Study Treatment Date IF AE Start Time is not collected
 

Open-Label Phase (4th Treatment)	
 
Fourth Study Treatment Date ≤ AE Start Date ≤ Final Visit Date AND Fourth Study Time ≤ AE Start Time IF AE Start Time is collected
 
Fourth Study Treatment Date ≤ AE Start Date ≤ Final Visit Date IF AE Start Time is not collected
 

Drug related	
 
If relationship to Study treatment(GSK1358820/Placebo) is marked 'YES' on CRF OR value is missing.
 

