No.	Population	IDSL / Example Shell	Title	Programming Notes	Deliverable
3.19.	Safety 1	AE5A	Summary of All Drug-Related Adverse Events until Week 24 visit by System Organ Class and Preferred Term and Maximum Intensity	ICH E3 Treatment Emergent AE See the Section 10.4.2 Three treatment arms (240, 400 and 240 + 400U)	IA SAC
3.20.	Safety 1	AE5A	Summary of All Drug-Related Adverse Events until Week 24 visit by System Organ Class and Preferred Term and Maximum Intensity in Blind Phase	Blind Phase (until second dose) See the Section 10.4.2 . Two treatment arm (240 and 400U)	IA SAC
3.21.	Safety 1	AE5A	Summary of All Drug-Related Adverse Events within 84 days from the initial dose by System Organ Class and Preferred Term and Maximum Intensity in Blind Phase	Blind Phase (within 84 days) See the Section 10.4.2 . Two treatment arm (240 and 400U)	IA SAC
3.22.	Safety 2	AE5A	Summary of All Drug-Related Adverse Events until Week 24 visit by System Organ Class and Preferred Term and Maximum Intensity in Open Label Phase (2nd Treatment)	Open Label Phase (2nd Treatment) See the Section 10.4.2 . Three treatment arms (240, 400 and 240 + 400U)	IA SAC
3.23.	Safety 1	AE15	Summary of Common (>=5%) Non-serious Adverse Events until Week 24 visit by System Organ Class and Preferred Term (Number of Participant and Occurrences)	FDAAA, EudraCT Treatment Emergent AE See the Section 10.4.2	IA SAC
Serious and Other Significant Adverse Events					
3.24.	Safety 1	SAFE_T1	Summary of Adverse Events of Special Interest until Week 24 visit	Treatment Emergent AE See the Section 10.4.2 Three treatment arms (240, 400 and 240 + 400U)	IA SAC

CONFIDENTIAL

207660

Safety: Tables					
No.	Population	IDSL / Example Shell	Title	Programming Notes	Deliverable
3.25.	Safety 1	SAFE_T1	Summary of Adverse Events of Special Interest until Week 24 visit in Blind Phase	Blind Phase (until second dose) See the Section 10.4.2 . Two treatment arm (240 and 400U)	IA SAC
3.26.	Safety 1	SAFE_T1	Summary of Adverse Events of Special Interest within 84 days from the initial dose in Blind Phase	Blind Phase (within 84 days) See the Section 10.4.2 . Two treatment arm (240 and 400U)	IA SAC

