No.	Population	IDSL / Example Shell	Title	Programming Notes	Deliverable
3.88.	Safety 2	AE5A	Summary of All Drug-Related Adverse Events by System Organ Class and Preferred Term and Maximum Intensity in Open Label Phase (2nd Treatment)	Open Label Phase (2nd Treatment) See the Section 10.4.2 . Three treatment arms (240, 400 and 240 + 400U)	SAC
3.89.	Safety 2	AE5A	Summary of All Drug-Related Adverse Events by System Organ Class and Preferred Term and Maximum Intensity in Open Label Phase (3rd Treatment)	Open Label Phase (3rd Treatment) See the Section 10.4.2 . Three treatment arms (240, 400 and 240 + 400U)	SAC
3.90.	Safety 2	AE5A	Summary of All Drug-Related Adverse Events by System Organ Class and Preferred Term and Maximum Intensity in Open Label Phase (4th Treatment)	Open Label Phase (4th Treatment) See the Section 10.4.2 Three treatment arms (240, 400 and 240 + 400U)	SAC
3.91.	Safety 1	AE3	Summary of Most Common Serious Drug Related Adverse Events by Overall Frequency in Overall Study Period	Three treatment arms (240, 400 and 240 + 400U)	SAC
3.92.	Safety 1	AE2	Summary of Most Common Non-Serious Drug Related Adverse Events by Overall Frequency in Overall Study Period	Three treatment arms (240, 400 and 240 + 400U)	SAC
3.93.	Safety 1	AE15	Summary of Common (>=5%) Non-serious Adverse Events by System Organ Class and Preferred Term (Number of Participant and Occurrences) in Overall Study Period	FDAAA, EudraCT Treatment Emergent AE See the Section 10.4.2 Three treatment arms (240, 400 and 240 + 400U)	SAC

CONFIDENTIAL

207660

Safety: Tables					
No.	Population	IDSL / Example Shell	Title	Programming Notes	Deliverable
Serious and Other Significant Adverse Events					
3.94.	Safety 1	SAFE_T1	Summary of Adverse Events of Special Interest in Overall Study Period	Treatment Emergent AE See the Section 10.4.2 Three treatment arms (240, 400 and 240 + 400U)	SAC
3.95.	Safety 1	SAFE_T1	Summary of Adverse Events of Special Interest in Blind Phase	Blind Phase (until second dose) See the Section 10.4.2 . Two treatment arm (240 and 400U)	SAC
3.96.	Safety 1	SAFE_T1	Summary of Adverse Events of Special Interest within 84 days from the initial dose in Blind Phase	Blind Phase (within 84 days) See the Section 10.4.2 . Two treatment arm (240 and 400U)	SAC

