3.107.	Safety 1	AE1	Summary of Drug-Related Non-Fatal Serious Adverse Events in Blind Phase	Blind Phase (until second dose) See the Section 10.4.2 . Two treatment arm (240 and 400U)	SAC
3.108.	Safety 1	AE1	Summary of Drug-Related Non-Fatal Serious Adverse Events within 84 days from the initial dose in Blind Phase	Blind Phase (within 84 days) See the Section 10.4.2 . Two treatment arm (240 and 400U)	SAC
3.109.	Safety 2	AE1	Summary of Drug-Related Non-Fatal Serious Adverse Events in Open Label Phase (2nd Treatment)	Open Label Phase (2nd Treatment) See the Section 10.4.2 Three treatment arms (240, 400 and 240 + 400U)	SAC
3.110.	Safety 3	AE1	Summary of Drug-Related Non-Fatal Serious Adverse Events in Open Label Phase (3rd Treatment)	Open Label Phase (3rd Treatment) See the Section 10.4.2 Three treatment arms (240, 400 and 240 + 400U)	SAC
3.111.	Safety 4	AE1	Summary of Drug-Related Non-Fatal Serious Adverse Events in Open Label Phase (4th Treatment)	Open Label Phase (4th Treatment) See the Section 10.4.2 Three treatment arms (240, 400 and 240 + 400U)	SAC

CONFIDENTIAL

207660

Safety: Tables					
No.	Population	IDSL / Example Shell	Title	Programming Notes	Deliverable
3.112.	Safety 1	AE16	Summary of Serious Adverse Events by System Organ Class and Preferred Term (Number of Participants and Occurrences) in Overall Study Period	FDAAA, EudraCT Treatment Emergent AE See the Section 10.4.2 Three treatment arms (240, 400 and 240 + 400U)	SAC
3.113.	Safety 1	AE1	Summary of Adverse Events Leading to Withdrawal from Study by System Organ Class and Preferred Term in Overall Study Period	IDSL Treatment Emergent AE See the Section 10.4.2 Three treatment arms (240, 400 and 240 + 400U)	SAC
3.114.	Safety 1	AE1	Summary of Adverse Events Leading to Withdrawal from Study by System Organ Class and Preferred Term in Blind Phase	Blind Phase (until second dose) See the Section 10.4.2 . Two treatment arm (240 and 400U)	SAC
3.115.	Safety 1	AE1	Summary of Adverse Events Leading to Withdrawal from Study within 84 days from the initial dose by System Organ Class and Preferred Term in Blind Phase	Blind Phase (within 84 days) See the Section 10.4.2 . Two treatment arm (240 and 400U)	SAC

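### Overall-study adverse-event tables count events after open-label 400-unit injections under 240U, and the FDAAA/EudraCT-tagged tables of serious and common non-serious events are planned only in that form

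*SAP*

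**What the plan says.** References are to the amended SAP (20 August 2018).

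- **Grouping.** Section 8.1: "Adverse events that occurred in the overall study period, blinded period and open-label period will be summarized for each treatment group". The next sentence fixes the column: "The treatment group is based on dose actually given in blind period". Section 4 says of the Safety populations: "The participants will be analyzed based on the treatment actually given". Section 8.1 settles what that means for someone who receives both doses: the first dose decides. Section 5.1 labels the columns GSK1358820 240U and GSK1358820 400U.
- **Treatment after the blind phase.** Section 2.3: "In the Open-label phase, a total of 400 units will be injected in both groups". Up to three open-label injections are allowed.
- **Window.** Section 10.4.2 defines treatment-emergent as "First Study Treatment Date ≤ AE Start Date ≤ Final Visit Date/Early Withdrawal Date", with no cut at the second injection. The same table defines a separate blind-phase flag that runs until the second dose, and another for 84 days.
- **Displays.** Section 10.12.7.2 lists Table 3.93, "Summary of Common (>=5%) Non-serious Adverse Events by System Organ Class and Preferred Term (Number of Participant and Occurrences) in Overall Study Period", and Table 3.112, "Summary of Serious Adverse Events by System Organ Class and Preferred Term (Number of Participants and Occurrences) in Overall Study Period". Both are tagged FDAAA and EudraCT, with columns 240, 400 and 240 + 400U. The interim counterparts in 10.12.7.1 are 3.36 and 3.23, the latter titled "Summary of Common (>=5%) Non-serious Adverse Events until Week 24 visit by System Organ Class and Preferred Term (Number of Participant and Occurrences)". Both are treatment-emergent. Tables 3.91 and 3.92 (most common serious and non-serious drug-related events) are also overall-study only.

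**The concern.** Comparing the safety of 400 units with that of 240 units is a secondary objective (2.2). A column headed 240U invites reading as a dose. In an overall-study table it is a sequence: one 240-unit injection, then up to three of 400 units. For every retreated participant, events from the second injection onward sit under a dose that the participant was no longer receiving.

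For most categories the reader can turn to a blind-phase table. For the AE15 shell (3.23, 3.93) and the AE16 shell (3.36, 3.112) there is none. The blind-phase serious-event tables (3.101, 3.102, 3.107, 3.108) cover non-fatal events only, so AE16 is the only summary table of all serious events, and it mixes the doses. No blind-phase table isolates non-serious events. AE15 and AE16 are also the only adverse-event summaries titled as giving occurrences, and occurrence counts grow with each further cycle.

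**Working it through.** The SAP gives no adverse-event rates and no figure on this point, so there is nothing to reproduce. Two quantities can be worked out: how much of the 240U column follows a 400-unit injection, and what that does to a contrast under stated assumptions.

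**1. Share of follow-up after an open-label 400-unit injection (240 group).** Inputs: final visit at Week 48 and first retreatment between Week 12 and Week 36 (10.2.1). Formula: (48 − w)/48, where w is the week of first retreatment.

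- w = 12: 36/48 = 75%
- w = 24: 24/48 = 50%
- w = 36: 12/48 = 25%
- never retreated: 0%

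For the interim tables with a nominal cut at Week 24, (24 − w)/24 gives 50% at w = 12, 33% at w = 16, 17% at w = 20, and 0% at w = 24 or later. Section 3.1 takes the cut-off visit for a Week 16 retreatment to be open-label Week 12, which is Week 28. That case then becomes 12/28 = 43%.

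**2. Effect on the contrast.** Assumptions, none from the SAP: independent cycles, risk q240 after a 240-unit injection, risk q400 after each 400-unit injection. With c cycles:

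- 240U column: 1 − (1 − q240)(1 − q400)^(c−1)
- 400U column: 1 − (1 − q400)^c

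With q240 = 5% and q400 = 10%:

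- c = 1 (blind phase only): 5.0% v 10.0%, ratio 2.00, difference 5.0 points
- c = 2: 1 − 0.95 × 0.90 = 14.5% v 1 − 0.90² = 19.0%, ratio 1.31
- c = 4: 1 − 0.95 × 0.90³ = 30.7% v 1 − 0.90⁴ = 34.4%, ratio 1.12, difference 3.6 points

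Range over other assumed risks, one cycle against four in both arms:

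| q240 / q400 | Ratio, 1 cycle | Ratio, 4 cycles | Difference (points), 1 to 4 cycles |
|---|---|---|---|
| 2% / 4% | 2.00 | 1.13 | 2.0 to 1.8 |
| 5% / 7.5% | 1.50 | 1.08 | 2.5 to 2.0 |
| 5% / 10% | 2.00 | 1.12 | 5.0 to 3.6 |
| 10% / 20% | 2.00 | 1.09 | 10.0 to 5.1 |

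**3. Unequal retreatment.** With 5% and 10%, four cycles in the 240 group and three in the 400 group, the columns read 30.7% v 1 − 0.90³ = 27.1%, ratio 0.88. With 5% at both doses and the same cycles they read 18.5% v 14.3%, ratio 0.77, although dose has no effect. With equal risks and equal cycles the ratio is 1.00 and nothing is distorted.

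**4. Which displays have a blind-phase version.** In the final list, tables of 240 against 400U exist both until the second dose and within 84 days for:

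- all events (3.62, 3.63) and maximum intensity (3.68, 3.69)
- common events at 3% (3.74, 3.75)
- drug-related events (3.80, 3.81; by intensity 3.86, 3.87)
- events of special interest (3.95, 3.96)
- non-fatal serious events (3.101, 3.102) and drug-related non-fatal serious events (3.107, 3.108)
- events leading to withdrawal (3.114, 3.115)

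None exists for 3.93, 3.112, 3.91 or 3.92, nor for 3.23 and 3.36 at the interim.

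**The case against.** The strongest reply is that the safety comparison is already answered elsewhere. Section 8.1 plans two blind-period analyses by dose and the display list delivers them, with open-label cycles tabulated separately. A reader might infer from the grouping rule that the trial's dose comparison of harms as a whole is diluted. The display list does not support that.

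A reader might also infer that the events in the four tagged tables have no crossover-free comparison at all. That goes too far. Common non-serious events lie within 3.63 and within 3.75, which uses a lower threshold. Non-fatal serious events are in 3.101 and 3.102. Fatal ones are in Listing 56 with their study phase. Drug-related events are in 3.80, 3.81, 3.107 and 3.108, which is why 3.91 and 3.92 matter less. What is missing is a blind-phase table of all serious events with fatal ones included, a table separating out non-serious events, and occurrence counts.

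Three further points stand. Dilution presumes a higher risk at 400 units and similar retreatment in both arms; the SAP establishes neither, and the contrast can reverse. The tags do not say what will be posted or in which columns, so it cannot be asserted that these exact columns become the public record. The final tables do carry the overall study period in their titles, and the grouping rule is stated openly.

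None of this removes the gap. The tagged tables exist only in mixed form, under labels that name a single dose.

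**Conclusion.** The point holds in a limited form. Tables 3.23/3.93 and 3.36/3.112, and with less consequence 3.91 and 3.92, set a 240U column against a 400U column although both contain events after 400-unit injections, and no blind-phase version is planned. For a 240-group participant first retreated between Week 36 and Week 12, 25% to 75% of the 48 weeks follows a 400-unit injection. Under the assumed risks, a ratio of 1.5 to 2.0 shrinks to 1.08 to 1.13 with four cycles in both arms. With four cycles against three, the 5%/10% case reverses to 0.88. These ratios illustrate the mechanism and do not predict the trial: the event risks, cycle counts and independence between cycles are all assumed. The study report's main dose comparison is not affected. This is an inexpensive improvement to specific displays.

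**What to change.** 1. Add versions of AE15 (3.23, 3.93) and AE16 (3.36, 3.112) by arm for the blind phase, using the until-second-dose window. For participants never retreated it should run to completion or withdrawal, as 8.1 states. An 84-day table alone is not enough: eligibility for retreatment is assessed up to Week 36, so an event after the 84-day window but before the second injection would fall in neither the blind-phase nor the open-label display. An 84-day version may stand beside it, as for the other categories, because the until-second-dose window can differ in length between arms.
2. Show the open-label events for these two shells separately.
3. Keep the overall-study versions, head their columns '240U then open-label 400U' and '400U then open-label 400U', and add a footnote that they are not a dose comparison. The same headings suit 3.91 and 3.92.
4. Program the until-second-dose flag on date and time together. As worded in 10.4.2, the clock-time condition stands apart from the date condition. Taken literally, it would exclude an event on an earlier day whose clock time is later than that of the second injection.

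The cost is a few extra runs of existing shells with flags already planned, plus new column headings. No new data are needed and nothing changes in the conduct of the trial.

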## CONFIDENTIAL

207660

Unless specified otherwise, the data up to Week 12 of treatment will be summarized during the double-blind period. This is because this study allows to re-treat. In other words, after 12 weeks, only participants who have a smaller MAS score would remain and the difference of the change from baseline in MAS between 240 units and 400 units would be attenuated. Therefore, the data up to Week 12 of initial treatment will be analysed as secondary statistical analyses. This is the case for exploratory analyses for open label period (i.e. the data up to week 12 of re-treatment will be summarized). Listing will include the data after week 12 of treatment/re-treatment.

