## CONFIDENTIAL

207660

V5 and neutralizing antibody tests will be performed. If V5 in Parts 2 and 3 is performed at Week 36 or later, after completion of V5, completion visit will be performed at Week 48.

- e. QRV is allowable to perform from initial injection to Week 36. Eligibility evaluation (QRV) will not be performed after Week 36.
- f. V5 must be performed at least 84 days after V1.
- g. The acceptable visit windows will be -14 to +4 days if QRV is performed at Week 36.
- h. Must be performed earlier than any other procedures
- i. Must be performed before injection of the product
- j. For inclusion/exclusion criteria, the items to be observed are different between screening phase and Day 1. For details, refer to Protocol Section 6.1 and Section 6.2.
- k. For MAS evaluation, the items to be evaluated differ depending on the treatment phase. For details, refer to Protocol Section 9.1.1.1.
- l. MAS evaluation will be followed by NRS evaluation. For NRS evaluation, items to be evaluated differ. For details, refer to Protocol Section 9.1.1.2.
- m. Body temperature, heart rate, and blood pressure will be measured as vital signs.
- n. Women of childbearing potential will be only performed. Serum hCG pregnancy test must be performed at screening, and urine hCG pregnancy test after randomization. The tests can be performed beyond the protocol specifications if an investigator considers to be necessary.
- o. For laboratory test items, refer to Protocol Section 12.2. Attachment 2. Fasting is not required for blood collection.
- p. Adverse events and serious adverse events collection period will be from the initial injection day (Day 1) to completion visit (FV).
- q. Neutralizing antibody testing is performed 3 times in each participant. The first test will be performed in screening phase, the second is at V5 in the blind phase, and the third is at completion visit.
- r. A participant who withdraws the study before 12 weeks after last injection will be performed.
- s. Perform if V5 in each treatment phase is at Week 48 after initial injection
- t. Not necessary to perform doubly as V1 assessment if the same assessment is performed at V5 or QRV. If V1 assessment or retreatment cannot be performed on the same day as V5 or QRV, MAS assessment should be performed again on the day of visit for the V1 assessment.

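### Final open-label AE percentages cover whole cycles of unequal length, so at equal risk cycle 4 can look safer than cycles 2 and 3

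*SAP*

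**What the plan says.** References are to the amended SAP (20 August 2018).

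- **Measure.** Section 8.1: "The number and percentages of participants who experience at least one AE will be presented". No person-time or exposure-adjusted rate is planned. Section 8.2 presents AESIs as number and percentage by cycle.
- **Blind phase.** Section 8.1 gives two counts. One runs to the first open-label dose. For the second, "another one is on adverse events that occurred within 84 days from the initial dose". Section 10.4.2 defines that window as the first treatment date to that date plus 83 days.
- **Open-label phase.** Section 8.1 lists whole cycles only, from "AEs occurred during 2nd treatment cycle" to "AEs occurred during 4th treatment cycle". In Section 10.4.2 the cycle 2 flag is "Second Study Treatment Date ≤ AE Start Date ≤ Third Study Treatment Date" and the cycle 4 flag is "Fourth Study Treatment Date ≤ AE Start Date ≤ Final Visit Date". The cycle 2 and 3 flags give no end date for a participant who receives no further dose.
- **Schedule.** Section 10.2.1 puts V5 at least 84 days after V1 (footnote f) and completion at Week 48 (footnote d). Footnote e adds: "Eligibility evaluation (QRV) will not be performed after Week 36".
- **Displays.** The final by-cycle tables (3.64–3.66 for all AEs, 3.82–3.84 drug-related, 3.97–3.99 AESIs, 3.103–3.105 non-fatal SAEs) use the whole-cycle flags. The matching 84-day tables (3.63, 3.81, 3.96, 3.102) cover the first injection only.

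**The concern.** The percentage of participants with at least one event grows with the time over which events are counted. If cycle 2 is followed for longer on average than cycle 4, its percentage will be higher even when the risk per week is the same. Safety and tolerability of 400 units is a secondary objective, and the by-cycle tables are where a reader will look for a change with repeated injection. The length difference works against cycles 2 and 3 and in favour of cycle 4, so it could hide an increase at the fourth injection, including in the respiratory and distant-spread AESIs. Nor can the whole-cycle percentages be read against the 84-day percentages for the first injection, because the follow-up differs.

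**Working it through.** **1. Cycle lengths from the schedule.** Inputs: doses at least 12 weeks apart, later evaluations every 4 weeks, no evaluation after Week 36, at most four doses, end at Week 48. The Section 2.3 diagram gives an open-label phase of 36 weeks, and 48 − 12 = 36 reproduces it. The first retreatment pattern in Section 10.3.1 (12 + 12 + 12 = 36) is the only route to a fourth dose. Enumerating every dosing path gives:

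| Cycle | Possible nominal lengths (weeks) |
|---|---|
| 2 | 12, 16, 20, 24, 28, 32, 36 |
| 3 | 12, 16, 20, 24 |
| 4 | 12 |

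The 28-, 32- and 36-week values require the cycle 2 flag to run to the Final Visit when there is no third dose. If cycle 2 counted only when closed by a third dose, its maximum would be 36 − 12 = 24 weeks.

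**2. Effect of length alone.** Assume a constant hazard with risk p per 84 days. Then risk(w) = 1 − (1 − p)^(w/12). The SAP gives no value for p, so a range is shown.

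| p | 12 weeks | 24 weeks | 36 weeks |
|---|---|---|---|
| 10% | 10.0% | 19.0% | 27.1% |
| 20% | 20.0% | 1 − 0.8² = 36.0% | 1 − 0.8³ = 48.8% |
| 30% | 30.0% | 51.0% | 65.7% |
| 50% | 50.0% | 75.0% | 87.5% |

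**3. Averaging over the paths.** These are single-length figures; a cycle mixes lengths. Assume each evaluation leads to retreatment with probability q (not in the SAP; 0.3 to 1.0 tried) and no withdrawals. The displayed percentage is the sum over lengths of the share of entrants with that length times risk(length).

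One piece of the sum, for q = 0.5, p = 20% and a second dose at Week 12: lengths 12, 16, 20 and 24 weeks have shares 0.5, 0.25, 0.125 and 0.0625, and the remaining 0.0625 runs 36 weeks. That gives 0.5×0.200 + 0.25×0.257 + 0.125×0.311 + 0.0625×0.360 + 0.0625×0.488 = 25.6%. Including the later second doses gives 26.1%.

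Results at p = 20%:

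| q | Mean weeks, cycles 2 / 3 / 4 | Displayed %, cycles 2 / 3 / 4 | Cycle 2 − cycle 4 | Share reaching cycle 4 (q³) |
|---|---|---|---|---|
| 1.0 | 12.0 / 12.0 / 12.0 | 20.0 / 20.0 / 20.0 | 0.0 | 1.000 |
| 0.9 | 12.4 / 14.4 / 12.0 | 20.6 / 23.2 / 20.0 | 0.6 | 0.729 |
| 0.7 | 13.9 / 16.8 / 12.0 | 22.6 / 26.6 / 20.0 | 2.6 | 0.343 |
| 0.5 | 16.6 / 17.2 / 12.0 | 26.1 / 27.2 / 20.0 | 6.1 | 0.125 |
| 0.3 | 20.2 / 16.9 / 12.0 | 30.6 / 26.7 / 20.0 | 10.6 | 0.027 |

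The largest drop (q = 0.3) is 16.0 − 10.0 = 6.0 points at p = 10%, 43.7 − 30.0 = 13.7 at 30% and 65.9 − 50.0 = 15.9 at 50%. Cycle 4 is never above cycle 2 or 3. Cycle 3 exceeds cycle 2 at q = 0.5 to 0.9. The largest drops occur where few reach cycle 4: at q = 0.3, 0.027 × 120 ≈ 3 participants.

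**4. With an 84-day window after every injection**, each cycle shows 20% at p = 20% whatever q is, provided each cycle uses its own Safety population. The existing drug-related tables for cycles 3 and 4 (3.83, 3.84, 3.89, 3.90) are assigned to Safety 2. At q = 0.7 that denominator turns cycle 4 into 0.343 × 20% = 6.9%.

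**The case against.** The strongest reply is that no comparison between cycles is planned. Section 5.1 names only 400 against 240 units, nothing is tested, and the open-label phase is uncontrolled. Safety 2, 3 and 4 are increasingly selected, and the muscles and dose split may change from cycle to cycle, so equal windows would not make the cycles fully comparable. Everyone who reaches cycle 4 had nominal 12-week cycles throughout, so within Safety 4 the lengths are already equal. Kaplan-Meier summaries of time to requalification (Tables 2.51–2.53) and the AE listing with phase flags let a careful reader see the problem.

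All of that stands, and it limits the point. It does not remove it: the tables are laid out by cycle, will be read across, and carry a length difference that the plan could remove.

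Three stronger readings are tempting, and the SAP does not support them:

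- A reader might infer that AE risk will appear to fall steadily with repeated injection. It need not: there is no distortion if everyone requalifies at 12 weeks, and cycle 3 can exceed cycle 2.
- A reader might infer from the single-length figures that cycle 4 would show a half to a third of the cycle 2 percentage. A 36-week cycle 2 means no third dose, so those participants never enter cycle 4; a cycle 2 made up only of them would leave cycle 4 empty.
- A reader might infer that the plan contradicts itself, because for efficacy "the data up to week 12 of re-treatment will be summarized". Section 7.2.3 gives a different reason for that cut: those still unretreated after Week 12 are a selected group with lower MAS scores. That concerns who remains, not how long events are counted.

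**Conclusion.** The point holds in limited form and for the final analysis only; the interim tabulates open-label AEs for the second treatment alone. Whole-cycle percentages with no fixed window or exposure adjustment can make cycle 4 look safer than cycles 2 and 3 at equal risk, and they are not comparable with the blind-phase 84-day rates.

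At an assumed 20% per 84 days, a constant hazard, no withdrawals and a requalification probability of 0.3 to 1.0, the cycle 2 to cycle 4 drop is 0 to about 11 points. The direction is fixed under these assumptions, but the size is not known: the SAP gives neither the event rate nor the distribution of retreatment times. Events clustering soon after injection would shrink it. The 36-week upper limit rests on reading the cycle 2 flag as running to the Final Visit, which Section 10.4.2 does not state. This is a worthwhile, inexpensive improvement to the safety displays; the efficacy analyses are unaffected.

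**What to change.** 1. Add to Section 10.4.2 a flag for events within 84 days of the 2nd, 3rd and 4th study treatment: treatment date ≤ AE start ≤ treatment date + 83 days, and before the next treatment.
2. Produce the final all-AE, drug-related AE, SAE and AESI tables by cycle on that flag, using Safety 2, 3 and 4 for cycles 2, 3 and 4 respectively.
3. Say that these are the tables for any reading across cycles or against Tables 3.63, 3.81, 3.96 and 3.102. Keep the whole-cycle tables for late-onset events.
4. State the end date of the cycle 2 and 3 flags (Final Visit or withdrawal) when no further dose is given.

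**Cost.** Four table types × three cycles = about 12 more tables, from existing data and programs. The fixed window removes the difference in follow-up length; it does not remove the selection of participants who reach later cycles, and the text around the tables should say so.
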